- Lack of a primary care physician who can be contacted if there are findings on the MRI.
- Presence of metal in the body (prostheses, electrodes, shrapnel, aneurism clips, other medical hardware)
- Presence of certain tattoos with ferromagnetic metal or permanent makeup, due to the exposure to high magnetic force through MRI procedures.
- Subjects who were metal workers as a previous occupation will also be excluded due to the possibility of unknown/undetected metal in their body.
- Volunteers with broken skin in the area that the fNIRS probes will be placed on the scalp
- Claustrophobia
- Previous surgery that used surgical staples
- Artificial joints

Will data be collected from or about any of the following populations?

Minors (under 18 years of age); Specify Age: 13 and over  
 Prisoners  
 Pregnant Women  
 Fetuses  
 Cognitively impaired persons  
 Other protected or potentially vulnerable population  
 Not Applicable

Passy-Muir Swallowing Self-Trainer

The Self-Trainer is designed to be used in either automatic or manual mode. The mode can be easily set using a switch on the side of the controller. When the controller is in automatic mode, the device will vibrate up to 15 seconds every 3-5 minutes. These specifications are set by connecting the Self-Trainer to a computer terminal by the investigators. When the controller is in manual mode, the device operates in a momentary manner, specifically the device only vibrates when the button is pushed.

Swallow Practice

[figure not shown]
The participant will practice swallowing with the Self-Trainer daily in their home environment for 3 months. The Self-Trainer device will be set to vibrate at a vibration rate and pressure that is ideal for each participant based on testing (see Procedures Part B, section g). The participant will wear the Self-Trainer during waking hours with the device in automatic mode. In automatic mode the Self-Trainer will be programmed to vibrate up to 15 seconds every 3-5 minutes to stimulate saliva swallows and promote swallowing practice. In this manner the participant will complete approximately 180-300 saliva swallows per day.

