#### D. Outcome measures

Outcome measures a-e will be completed at the SRMH Voice and Swallowing Services in the Treatment Center. Voice and Swallowing Service is a collaboration between SRMH Healthcare and James Madison University.

- a. Training and maintenance data will be taken on each participant and will include how many training sessions were required to demonstrate competency for device use, the duration of each training session, caregiver involvement, documentation of questions or comments during maintenance phone calls, and how many times the participant contacted the research team and for what purposes.
- b. Participant feedback will be gathered at the end of the 3 month self-training period. The participant will read or be read a series of multiple choice questions (Appendix K) regarding their opinion on the training they received, ease of device use, and design of the device. The participants will be instructed to answer truthfully and will be assured that their answers will not impact their treatment or enrollment in this or future research studies at JMU/SRMH.
- c. Participant fidelity will be measured by 1) daily documentation by the participant or caregiver on device use and 2) downloading the count data from the device periodically throughout the study which provides data on how many times the device has vibrated in automatic mode and in manual mode.

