For participants who take food orally these consistencies must be approved by the SLP as being safe to use with the device. If the participant is not safe for any intake, instructions will be given to remove the device from the participant's neck prior to food consumption they take for pleasure. As the Self-Trainer is known to increase the frequency of swallowing, the participants will be swallowing their secretions more frequently and therefore it is possible that each participant's risk of aspirating could change. For some participants, specifically those who do not swallow their secretions and instead periodically expectorate, the participant is now attempting to swallow the secretions instead of attempting to clear them from their oropharynx using regurgitation. Participants who do not feel secretions pooling in their throat may have a decreased risk of aspirating secretions while using the device as they are now prompted to swallow. As saliva swallows and the risks associated with saliva aspiration are an ongoing daily risk for these participants, this study provides only a minimal increase in risk. Efforts will be made to minimize any risk associated with participation in this study (see Protection against risks). If a participant expectorates their saliva as a part of reducing aspiration risk, they will be encouraged to continue with this practice as needed, but to try to swallow when they feel the urge to swallow as part of the self-training. The study will be conducted by a licensed speech language pathologist who will counsel each participant on minimizing secretion aspiration risk.

Participants will be encouraged to continue with their current swallowing treatment plan of care as determined by their speech language pathologist. We will take great care to make certain that all participants and their family and caregivers do not misinterpret the purpose of this research and fully understand that this study is experimental research with no guarantees of benefit. It will be made clear in the advertising material, informed consent and in any discussions with the participants and family members that treatment received is experimental research and there is no guarantee of improvements in swallowing function. The speech language pathologist conducting the research will provide participants and their

caregivers with referrals to patient services in their area for treatment of their swallowing disorder if appropriate.

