#### **B. Human Subjects Protection- Recruitment and Informed Consent**

Participants will be recruited through community hospitals, rehabilitations, and home health services. We will recruit from area speech language therapy service centers by placing advertisements in the waiting areas and asking professionals including neurologists, otolaryngologists, and speech-language pathologists to place notices in their waiting and office areas. Notices will also be mailed to professionals involved in rehabilitation in the Shenandoah Valley area asking them to place notices in their waiting and office areas. We will also be using email blasts, discussion board postings, and a website ([swallowselftrainer.com](http://swallowselftrainer.com)) to increase awareness of the study among speech language pathologists and patients with swallowing disorders in the community. We will only ask professionals to place notices and make literature available on our study but not to refer patients directly to us so patients will not feel under any undue influence from their professional caregivers to participate. Our notices and literature will provide information that will allow participants to contact us directly and the website will allow patients to self-refer.

We have 3 rooms in the JMU-SRMH Voice and Swallowing Service to support multiple participants being tested simultaneously. Free parking is immediately available within 100 ft of the entrance to our testing rooms in the Treatment Center on the ground floor of SRMH. The burden to participants will be the daily use of the Self-Trainer for 3 months, the majority of which the device will be switched in "automatic" mode requiring no active engagement on the part of the participant. Active practice required of the participant consists of 60 swallows and will take from 30-60 minutes a day. Additional burden to the participant includes 3 or more visits to SRMH for testing measures, while periodic counts taken from the Self-Trainer can be completed with laptops and can be done in the participant's home, JMU or SRMH as is convenient. Weekly check ins can be done over the telephone, Skype, or as needed by the participant to answer questions and verify compliancy, although in person appointments can be made if needed.

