**C. Protection against risk**

As listed above under Potential Risks, this application is expected to involve only minimal increased risk from the research procedures for participants with swallow disorders as only saliva swallows or 1-2 ml water swallows as needed (equivalent to a saliva swallow) will be used while the device is on. All participants will be producing saliva normally and will be exposed to the risk of saliva aspiration throughout the day in their normal living. This risk occurs even when they are receiving enteral feeding either through a PEG tube or nasogastric tube. With the increased frequency in swallowing associated with the Self-Trainer, there is a minimal increased risk for the participant because of their swallowing disorder.

To minimize the risk associated with saliva aspiration, the speech language pathologist conducting the research will train all participants and their caregivers on a daily regimen to follow for secretion aspiration prevention and an oral hygiene regime to reduce oral bacteria. Each participant and their caregivers will be trained to competency on the following aspiration monitoring methods:

1. Oral hygiene including cleaning the mouth, teeth (or dentures), tongue, etc. with toothpaste and mouthwash, as deemed appropriate, after meals or 3 times a day.
2. Voice quality testing to detect a wet, gurgly voice quality which would indicate increased fluid in or around the airway. If voice quality sounds “wet” they will be trained to voluntarily move secretions away from the airway by throat clearing/coughing to bring the secretions in the mouth and then spitting or swallowing the materials brought up.
3. Daily body temperature monitoring: The participant and their caregivers will be instructed to contact the research staff if they have a rise in body temperature over three days sequentially while participating in the study.
4. Participants and caregivers will be instructed to only use the Self-Trainer while sitting in an upright position, which may be helpful in preventing the aspiration of oral secretions. If the participant needs to lay down for any reason, the Self-Trainer should be switched off and/or removed from the participant’s neck. They will also be instructed not to use the self-trainer during vigorous exercise (like running) as this would be cumbersome and could result in damage to the device.

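### The automatic-mode vibration count records time powered on, not time on the neck, so as a fidelity measure it can overstate wear

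*Protocol*

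**What the plan says.** Under D. Outcome measures, item c, the Protocol takes fidelity from two sources. One is "daily documentation by the participant or caregiver on device use". The other is a periodic download from the device of "how many times the device has vibrated in automatic mode and in manual mode".

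The two modes are triggered differently (Passy-Muir Swallowing Self-Trainer):
- Automatic: "When the controller is in automatic mode, the device will vibrate up to 15 seconds every 3-5 minutes". Section B, Recruitment and Informed Consent, describes this mode as "requiring no active engagement on the part of the participant".
- Manual: "the device only vibrates when the button is pushed".

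Four places deal with the device being off the neck or out of automatic mode:
- Participant and Caregiver Instruction has the device put on after breakfast and worn in automatic mode while awake, except at meals, during swallowing practice and during vigorous exercise. It does not mention switching off.
- A. Potential Risks, for participants who are not safe for any intake but eat for pleasure: "instructions will be given to remove the device" beforehand. Switching off is not mentioned.
- C. Protection against risk, item 4, on lying down: "the Self-Trainer should be switched off and/or removed".
- C. Protection against risk, item 5, for those unsafe on all consistencies: the device is not to be worn with food in the mouth. Switching off is not mentioned.

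**The concern.** A timer-driven counter with no wear signal counts every cycle while it is powered in automatic mode, whether the motors rest on the larynx or the device lies on a table. Item 4 of C. Protection against risk is satisfied by removal alone. A participant who follows the instructions can therefore generate counts with no stimulation delivered, and no non-adherence need be assumed.

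This matters because of what the study is for. The Design paragraph lists how often the device is used, and compliance with the training guidelines, among the things the case series evaluates, and says that the results will settle use parameters before a Phase II controlled trial. The diary and the weekly contacts rest on what participants and caregivers report. The counter is the only device-recorded source. If it errs, it errs in the direction an optimistic diary would, so the two could agree and both be too high. Later analysis cannot recover on-neck time that was never recorded.

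**Working it through.** **Inputs from the Protocol**
- Automatic interval: 3 to 5 minutes (Passy-Muir Swallowing Self-Trainer).
- Intended automatic-mode swallows: about 180 to 300 per day (Swallow Practice).
- Planned manual practice: 60 swallows per day (Swallow Practice).

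**Inputs not in the Protocol**
- Powered hours per day in automatic mode: derived below.
- Hours per day off the neck but switched on: assumed, 1 to 2.5 h, with a wider range shown.

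**Step 1. Reproduce the plan's own figure.** Counts per day = hours × 60 / interval in minutes.
- 5-minute interval: 15 × 60 / 5 = 180.
- 3-minute interval: 15 × 60 / 3 = 300.

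The stated 180 to 300 is exactly 15 powered hours divided by the interval. Other day lengths give 144 to 240 (12 h) and 192 to 320 (16 h). If the 15 seconds of vibration were added to each interval, 15 h would give 171 to 277. The Protocol's own figure thus behaves as powered time divided by interval. Nothing in it depends on wear.

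**Step 2. Counts per unworn, powered-on hour.** 60 / 5 = 12 and 60 / 3 = 20.

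**Step 3. Effect on a 15-hour powered day.** With *u* unworn, powered-on hours, the extra counts are 12*u* to 20*u*, the false share of the log is *u*/15, and wear is overstated by *u*/(15 − *u*).

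| *u* (h/day, assumed) | Extra counts/day | False share of log | Overstatement of wear |
|---|---|---|---|
| 0.5 | 6–10 | 3.3% | 3.4% |
| 1 | 12–20 | 6.7% | 7.1% |
| 2 | 24–40 | 13.3% | 15.4% |
| 2.5 | 30–50 | 16.7% | 20.0% |
| 4 | 48–80 | 26.7% | 36.4% |

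The percentages do not depend on the interval, because it cancels.

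**Step 4. Direction.** Unworn running time adds counts and removes none, so the error from this source is never downward.

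**Step 5. Manual mode.** A manual count needs a button press, so a device left lying unworn does not add to it. It covers 60 planned swallows a day against 180 to 300 in automatic mode, so it says nothing about the larger part of the regimen.

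**The case against.** Several points on the other side are sound.

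- *Nothing shows that participants leave the device running.* This stands. A reader might infer that compliance will be overstated. The documents show only that it can be.
- *Mealtimes may contribute little.* This largely stands. The exception in Participant and Caregiver Instruction groups meals with swallowing practice, during which the device is worn in manual mode, so it may mean only that automatic mode is not used. A. Potential Risks and item 5 of C. Protection against risk also let some participants eat approved consistencies with the device on. A reader might add up three full meals plus an hour lying down and reach 3 hours or more a day. That does not fit a device first put on after breakfast, and the explicit removal instruction before eating reaches only a subgroup.
- *A device left on a table for 15 hours would log 180 to 300 and look like full compliance.* The arithmetic is true, but that participant is breaching the wear instructions. The example shows what the counter cannot detect, not an effect of the wording.
- *There are other checks.* The diary may be kept by a caregiver. Calls are daily for the first 3 days and weekly afterwards, and the weekly check-ins are partly to verify compliance. So fidelity does not rest on the counter alone. But these checks are all reported, and none measures wear independently.
- *The Protocol never calls the count objective or calls it wear time.* Correct: it is described as a number of vibrations. The difficulty is its use as a fidelity measure without on-neck time beside it.
- *Analysis rules and training materials are not shown.* How counts and diary are reconciled could sit in an analysis plan, and switching off could be covered in the written directions or the examiner's checklist. The first point does not help if on-neck time is never captured. The second may narrow the gap, but the Protocol's own wording still permits removal alone.
- *No compliance threshold is stated and no planned analysis is conditioned on the count.* This stands and limits the severity.

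**Conclusion.** The point holds in a limited form. As described, the automatic-mode count measures time powered on in automatic mode. It can overstate wear, and cannot understate it for this reason, by 12 to 20 counts for each unworn, powered-on hour. At an assumed 1 to 2.5 such hours in 15 powered hours a day, about 7% to 17% of logged counts would be false. The 15 hours is implied by the Protocol's own 180 to 300; the unworn hours are an assumption, and the true size is unknown.

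The conclusion also rests on there being no wear sensing in home use. None is described: the accelerometry and plethysmography belong to motor selection.

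A reader might also infer that the manual count should become the main fidelity figure. The documents do not support that. It covers only active practice, and a button press shows neither that the device was worn nor that a correctly timed swallow followed. This is a cheap improvement to data capture in a case series of 12 to 20 participants, not a flaw that undermines it.

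**What to change.** 1. In D. Outcome measures, item c, have the existing daily diary record the times at which the device is put on and taken off.
2. For each download period, compare the automatic count with the count expected from those times: recorded on-neck hours in automatic mode × 60 / that participant's programmed interval in minutes. An excess points to unworn running or to an inaccurate diary.
3. Report the automatic count as powered-on time, next to the diary's on-neck time.
4. Report the manual count against the planned 60 per day as a separate measure of active practice, not as a replacement.
5. Add to the device-use training and the examiner's checklist that the controller is off when it is not on the neck.
6. Ask the investigators to reconcile the removal, not-wearing and switch-off wording across Participant and Caregiver Instruction, A. Potential Risks, and items 4 and 5 of C. Protection against risk. When the device is worn should not change, and the final wording is theirs.

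The cost is a slightly longer diary entry and one extra step on removal. The on-neck times remain reported data, so the comparison shows up disagreement but does not prove wear.

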#### Human Subjects Protection

##### A. Potential Risks

During this case series, the participants are asked to wear the swallowing Self-Trainer around their neck to provide vibratory stimulation to the nerves that influence swallowing. They will wear the device during waking hours and prior research has shown that the stimuli can increase the frequency of swallowing 2-3x their normal rate. Participants will be instructed to only take food or liquid consistencies by mouth for nutritional purposes as recommended by the SLP based on their modified barium swallow while the device is on for swallowing training. Rather, the participants will swallow their own saliva or an equivalent amount of water (1-2 ml) as a part of the self-training, as they do on a normal basis throughout the day. As the most persons use up their saliva after 3 swallows, participants will be given a small syringe or ¼ teaspoon for administering 1-2 ml of water, equivalent to a saliva swallow, to moisten their mouths while practicing.

For participants who take food orally these consistencies must be approved by the SLP as being safe to use with the device. If the participant is not safe for any intake, instructions will be given to remove the device from the participant's neck prior to food consumption they take for pleasure. As the Self-Trainer is known to increase the frequency of swallowing, the participants will be swallowing their secretions more frequently and therefore it is possible that each participant's risk of aspirating could change. For some participants, specifically those who do not swallow their secretions and instead periodically expectorate, the participant is now attempting to swallow the secretions instead of attempting to clear them from their oropharynx using regurgitation. Participants who do not feel secretions pooling in their throat may have a decreased risk of aspirating secretions while using the device as they are now prompted to swallow. As saliva swallows and the risks associated with saliva aspiration are an ongoing daily risk for these participants, this study provides only a minimal increase in risk. Efforts will be made to minimize any risk associated with participation in this study (see Protection against risks). If a participant expectorates their saliva as a part of reducing aspiration risk, they will be encouraged to continue with this practice as needed, but to try to swallow when they feel the urge to swallow as part of the self-training. The study will be conducted by a licensed speech language pathologist who will counsel each participant on minimizing secretion aspiration risk.

Participants will be encouraged to continue with their current swallowing treatment plan of care as determined by their speech language pathologist. We will take great care to make certain that all participants and their family and caregivers do not misinterpret the purpose of this research and fully understand that this study is experimental research with no guarantees of benefit. It will be made clear in the advertising material, informed consent and in any discussions with the participants and family members that treatment received is experimental research and there is no guarantee of improvements in swallowing function. The speech language pathologist conducting the research will provide participants and their

caregivers with referrals to patient services in their area for treatment of their swallowing disorder if appropriate.

During the Modified Barium Swallow study the participant will be exposed to small amounts of radiation. As we are testing a minimum of 2 and a maximum of 12 swallows for each test, it is expected that the amount of radiation the participant will be exposed to will be negligible.

MRI does not involve radiation and is safe when used on individuals who are appropriately screened for the procedure. The FDA has classified MRI as a class II risk. Individuals with any implanted metal objects in the brain or body are at risk of injury with MRI procedures due to the high magnetic force to which they are exposed. Therefore, individuals with one or more of the MRI exclusion criteria will be excluded from the study. The principal investigator will review each of the exclusion criteria with the participant. Acoustic noise is generated in the magnet when the gradient coils are energized and de-energized in the magnetic fields to create MRI images. Subjects will be required to wear earplugs during the scan, which will be placed by the investigators. No incident of hearing impairment has been reported before in clinical scanners. During the scan, the investigator will monitor the patient's comfort level. We consider that the procedures described above are safe and should not produce any undue discomfort for subjects. The main discomfort associated with the study is the need for the subject to remain quiet within the scanner for the duration of testing, about 20 minutes maximum.

